The universe of the study was composed of women who had vaginal births in the City Hospital between years 2017-2018. According to the hospital records, in the first 6 months of 2017, the total number of births was determined as 1455, and the number of non-invasive vaginal births was 590. The minimum number of individuals to be included in the sample of the study was calculated using the "G-power 3.1.3" program based on the data of the study titled "The effect of antenatal training based on strengthening breastfeeding self-efficacy perception and breastfeeding success" (Tokat Aluş & Okuş, 2013). Considering the sample size of the research and the mean scores obtained from this study, the LACTH scale scores will increase 0.5 points after the application, with the pre-acceptance of the clinical effect to be 5% of Alpha error and 80% of the power of the study (Effect Size: 0.70) and it was determined that there should be at least 31 people in each group (Tokat Aluş & Okumuş, 2013). A total of 80 women, 40 studies and 40 control groups, were included in the sample. Women who had vaginal births meeting the inclusion criteria were selected by simple random randomization into the intervention and control group.

Randomization

Considering the inclusion and exclusion criteria, women were divided into simple randomization intervention and control groups. In the randomization of the sample, "Research Randomizer" was used. The randomization process was created by a neutral researcher who was not involved in the study. The women were not informed about the groups they were in. Single blind was provided in the study by knowing which group they would be in by the researcher.

Intervention

The study was carried out in two stages. In the first stage, in the first 24 hours at the postpartum period, the researcher interviewed the women who gave birth in the postpartum care units of the hospital and

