Based on the literature information (Faridvand, Mirghafourvand, Malakouti, & Mohammad-Alizadeh-Charandabi, 2017; Jeon & Hwang, 2013; Maleki-Saghooni et al., 2017; Tarrant, Younger, Sheridan-Pereira, & Kearney, 2011) an information form was developed by researchers. The form consisted of a total of 28 questions, including the socio-demographic and personal characteristics of women in the intervention and control group (16 questions), questions related to birth, postpartum period and

breastfeeding (12 questions). “LATCH Breastfeeding Diagnosis and Evaluation Scale” and “Postpartum Breastfeeding Self-Efficacy Scale Short Form” were used to evaluate breastfeeding success. The Breastfeeding Training Guide used in the education of mothers was created by scanning the literature on the subject (Aittasalo et al., 2006; Badaczewski et al., 2017; Farris, 2015; Tamura-Lis, 2013; Tokat, Okumuş, & Dennis, 2010) and in line with the recommendations of 5 academics specialized in Obstetrics and Gynecology Nursing. In order to evaluate the performance of the researcher using the Teach-back method, the “Teach-Back Method Observation Tool” recommended by the developers of this method was used.

Data Collection

In the first stage of the study, women were interviewed in postpartum care units, and when the health condition of the mother and baby was stable, the Personal Information Form was applied to the mothers.

In the second stage of the study, 3 interviews were conducted with the mothers in the intervention and control groups during the 2-5th postpartum days, 13-17th days and 30-42nd days. In the first meeting of the second phase, the pre-education Breastfeeding Diagnostic Tool LATCH and Postpartum Breastfeeding Self-Efficacy Scale were applied to the mothers in the intervention and control groups. Breastfeeding training and counseling services were provided to the mothers in the intervention group, based on the teach-back method, and those in the control group using the standard breastfeeding training technique. This interview lasted an average of 1 hour.

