In the second meeting of the second stage, which was held between the 13th and 17th days of birth, the pre-education Breastfeeding Diagnostic Tool LATCH and Postpartum Breastfeeding Self-Efficacy Scale were applied to the mothers in the intervention and control groups. Breastfeeding training and counseling services were provided to the mothers in the intervention group, based on the teach-back method, and those in the control group using the standard breastfeeding training technique. This interview took an average of 40-45 minutes.

In the third meeting of the second stage, which was held between the 30-42th days of birth, the pre-education Breastfeeding Diagnostic Tool LATCH and Postpartum Breastfeeding Self-Efficacy Scale

were applied to the mothers in the intervention and control groups. Breastfeeding training and counseling services were provided to the mothers in the intervention group, based on the teach-back method, and those in the control group using the standard breastfeeding training technique. This interview took an average of 40-45 minutes.

Statistical analysis

The data of the study were evaluated on computer by using Statistical Package for Social Sciences (SPSS) (22.0) program. In the evaluation of the data;

- The distribution of the data was evaluated with the Kolmogorov-Smirnov test. Since it showed a normal distribution, parametric tests were used in the analyzes.
- The homogeneity of the groups was assessed by chi-square test in categorical variables, Mann Whitney U in numerical variables, or T test in independent groups.
- In the intervention and control groups, “Multifaceted Variance Analysis in Repeated Measurements” was performed in comparing the LATCH breastfeeding diagnosis and evaluation scale and the breastfeeding self-efficacy scale according to the group, time and group * time interaction.
- In the advanced analysis of the difference between the LATCH, breastfeeding diagnostic and evaluation scale, and breastfeeding self-efficacy scale averages in the intervention and control groups, “One-Way Variance Analysis in Repetitive Measurements” to compare the mean scores of the groups within themselves, “Bonferroni Correction Dependent Groups T-Test” to compare the measurements with each other.

Ethical consideration

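### The group main effect averages in the pre-training score, so it understates the effect of training; H1 should rest on a baseline-adjusted comparison over meetings 2 and 3

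*SAP*

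**What the plan says.** Both scales are given at three meetings (days 2-5, 13-17 and 30-42). The SAP's Data Collection section places the first administration ahead of any teaching: "In the first meeting of the second phase, the pre-education Breastfeeding Diagnostic Tool LATCH and Postpartum Breastfeeding Self-Efficacy Scale were applied". At each later meeting the scales again come before that day's session.

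The Statistical analysis section lists one between-group analysis of these outcomes, a repeated-measures ANOVA "according to the group, time and group * time interaction". The follow-up steps are a one-way repeated-measures ANOVA "to compare the mean scores of the groups within themselves" and Bonferroni-corrected paired t-tests. The first-meeting score is neither excluded from the model nor used as a covariate. H1 is not tied to any model term or time point.

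The Sample size calculation section assumes that "the LACTH scale scores will increase 0.5 points after the application", with "Effect Size: 0.70", and enrols 40 women per arm.

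**The concern.** A score taken before training cannot show a training effect. When it is one of three levels of the outcome, the group term averages an expected zero with two informative differences. A reader who takes that term as the answer to H1 sees a smaller effect and, in most scenarios, a test weaker than the study was sized for.

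The interaction does not share this dilution. However, it is an omnibus test on 2 degrees of freedom: it gives no single effect in scale points and makes less efficient use of the baseline. The follow-up tests stay within each arm. No listed step therefore estimates the between-arm difference after training, which is what H1 is about.

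**Working it through.** **Inputs from the SAP.** Effect size 0.70, alpha 5%, power 80%, at least 31 per group, 40 per group enrolled, 0.5 LATCH points, three meetings.

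**Assumed, because the SAP does not give them.** Two-sided testing; equal SDs; the same correlation r between any two meetings, varied over 0.3, 0.5 and 0.7; the time-course of the effect; and 0.70 SD as the largest between-group difference.

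**The plan's own figure.** n = 2 × ((1.96 + 0.84)/0.70)² ≈ 32.04, so 33 per group by the normal approximation, or 34 by the two-sample t-test. The stated 31 is close but not exact. At 40 per group a two-sample t-test at a single time point has 87% power for 0.70 SD.

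**Dilution.** This step does not depend on r.
- Effect sustained: (0 + 0.70 + 0.70)/3 = 0.467 SD, two-thirds of 0.70. In points, 0.5 × 2/3 = 0.33.
- Half the effect at one later meeting: (0 + 0.35 + 0.70)/3 = 0.35 SD, half the peak. In points, 0.5 × 1/2 = 0.25.

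**Power formulas** (n = 40 per arm, SD 1)
- Group term: d = mean of the three differences / √((1+2r)/3); noncentral t, 78 df.
- Interaction: noncentral F, 2 and 156 df, λ = (n/2) × Σ(difference − mean difference)² / (1−r).
- Baseline-adjusted mean of meetings 2 and 3: d = mean of the two later differences / √((1+r)/2 − r²); noncentral t, 77 df.
- ANCOVA at days 30-42 alone: d = third-meeting difference / √(1−r²); noncentral t, 77 df.

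**Example** (sustained effect, r = 0.5)
- Group term: 0.467/√(2/3) = 0.572, power 71%.
- Interaction: λ = 20 × 0.3267/0.5 = 13.07, power 90%.
- Adjusted mean: 0.70/√(0.75 − 0.25) = 0.990, power 99%.

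**Power (%) at r = 0.3 / 0.5 / 0.7**

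| True differences at meetings 1, 2, 3 (SD) | Group term | Interaction | Adjusted mean of 2 and 3 |
|---|---|---|---|
| Sustained: 0, 0.70, 0.70 | 81 / 71 / 64 | 78 / 90 / 99 | 98 / 99 / 99.9 |
| Gradual (0, 0.35, 0.70) or fading (0, 0.70, 0.35) | 56 / 47 / 41 | 65 / 80 / 96 | 87 / 91 / 97 |
| One later meeting only | 29 / 24 / 21 | 78 / 90 / 99 | 54 / 59 / 73 |

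The day 30-42 ANCOVA alone has 90 / 95 / 99% for the sustained or gradual profile, but 37 / 43 / 58% if the effect fades.

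Simulation of the sustained, gradual and fading profiles (4,000 trials per cell) agreed with these formulas to within about 1 point. With no effect, every test rejected in 4.1 to 5.3% of trials.

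**The case against.** The plan never says that the group term decides H1. It lists the interaction beside it, and the interaction is a valid test with no type I error problem, so one sentence naming it would remove the ambiguity. **This stands**, and it is why the point concerns efficiency and clarity, not validity.

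No contrast is best everywhere. **This also stands.**
- The adjusted mean gains about 20 points over the interaction at r = 0.3, but only 1 to 2 at r = 0.7 and nothing at r = 0.8.
- It loses clearly if only one later meeting shows an effect. A late effect is plausible, because the second-meeting score follows one session and the third follows two.
- For a gradual effect, the day 30-42 ANCOVA is slightly better than the adjusted mean.
- With a sustained effect at r = 0.3, the group term reaches 81%, above the interaction's 78%.

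Three further cautions apply. The 0.5 points may have been meant as a within-group gain. The first-meeting score is collected after randomisation by a researcher who knows the allocation, so the expected zero assumes that this knowledge and any earlier contact did not affect it. Choosing a new deciding contrast once the data exist adds analytic flexibility, which disclosure reduces but does not remove.

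None of this rescues the group term. Its estimate is diluted in every profile, and it has the lowest power of the three in every cell but one.

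**Conclusion.** The concern holds. Given no expected difference before training, the group term estimates exactly two-thirds of the mean post-training difference. This further assumes only that the first-meeting score enters the ANOVA, which follows from three measurements, a time factor and no stated exclusion.

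The power loss depends on the unstated correlation and time-course. For a sustained, gradual or fading effect, the group term trails the adjusted mean by about 18 to 56 percentage points over r = 0.3 to 0.7. It reaches the planned 80% in only one cell of the table.

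The planned analysis is not invalid, because the interaction tests H1 properly. The fault is that the deciding term is left open, one candidate is diluted, and a baseline already in hand is not used for adjustment. This should be changed.

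**What to change.** Fit a model, for example SPSS MIXED, with the second- and third-meeting scores as outcomes, the first-meeting score as covariate, and group, visit and group-by-visit as terms. Name the baseline-adjusted group difference averaged over the two later meetings as the contrast that tests H1. Report it and the day 30-42 difference in scale points with 95% CIs. Do not interpret the group main effect that includes the first meeting. If the ANOVA is retained, state that group-by-time is the term that tests H1.

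The cost is one covariate degree of freedom and a re-analysis of data already collected. Because the SAP describes a completed study, the change must be labelled as made after the fact and shown beside the planned ANOVA. The price in power falls where the effect is confined to one later meeting: 54 / 59 / 73% for the averaged contrast against 78 / 90 / 99% for the interaction.

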determined the women who volunteered to participate in the research and that comply with the inclusion criteria and received their informed consent. Women were divided into randomized intervention or control groups. When the postpartum mother and baby's health condition was stable, "Personal Information Form" was applied to mothers. After the women were informed about the appointments and dates at the Family Health Centers where the second phase of the research will be carried out, the home and mobile numbers of the researcher were given to them in writing. The meeting ended with the mothers about the time and place of the next visits.

In the second stage of the study, three interviews were held with the mothers on the dates determined in the first stage of the study. In these interviews, the mothers in the intervention group were asked by the researchers about the needs of breastfeeding by using the relevant literature (Ekşioğlu, 2016; Hannula, Kaunonen, & Tarkka, 2008; Maleki-Saghooni et al., 2017; RNAO, 2018). Training and counseling based on the Teach-back method was given in the Family Health Centers (FHC) where they are registered. Turkey Ministry of Health's Postpartum Care Management Guidelines (2014) was carried out with mothers enrolled in FHC in the control group, on the basis of three interviews. In these interviews, standard training and counseling services were offered on breastfeeding. While providing standard training and counseling services, "Breastfeeding Training Guide" used in the intervention group was taken as the basis. The method of straight expression, which is mostly used by breastfeeding counseling provider healthcare professionals in Turkey, was used. In standard education, whether the learning is achieved is tested by closed-ended, "yes-no" questions structured as "Did you understand?". After, it is controlled by asking whether there are any questions about the subject. The trainings of both groups were given individually in a separate room at FHCs.

Measurements and data collection

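### The follow-up to the group-by-time test compares visits only within each arm, so no between-arm difference at day 13–17 or day 30–42 is tested or estimated

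*SAP*

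**What the plan says.** Under Statistical analysis, the SAP gives four items.

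- A Kolmogorov-Smirnov check of the distribution.
- Tests of group homogeneity, using chi-square and "Mann Whitney U in numerical variables, or T test in independent groups". This is the only place where a two-sample test is named.
- A repeated-measures ANOVA of LATCH and breastfeeding self-efficacy "according to the group, time and group * time interaction".
- A further analysis, introduced by "In the advanced analysis of the difference between the LATCH" and covering both scales in the two arms. It consists of a one-way repeated-measures ANOVA "to compare the mean scores of the groups within themselves" and Bonferroni-corrected dependent-groups t-tests "to compare the measurements with each other".

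Three other sections bear on the point.

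- Data Collection: the scales are given at days 2–5, 13–17 and 30–42, and the first of these precedes any training ("In the first meeting of the second phase, the pre-education Breastfeeding Diagnostic Tool LATCH").
- Intervention: the control arm's standard training also draws on the Breastfeeding Training Guide ("used in the intervention group was taken as the basis").
- Sample size calculation: the target is that "the LACTH scale scores will increase 0.5 points after the application", with effect size 0.70, 5% alpha and 80% power.

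**The concern.** The trial asks whether teach-back education does better than standard education. The interaction term answers yes or no. With two arms and three visits it is an F test on 2 numerator degrees of freedom, and it gives no visit, direction or size. A follow-up analysis should supply these, but the one named here looks only inside each arm.

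Two things are at stake. First, the quantity behind the sample size, a 0.5-point LATCH effect, is not estimated as a difference between arms at any visit after training has begun. Second, the follow-up is presented as the analysis of the difference, which invites the reading that a significant change in one arm and a non-significant change in the other shows a teach-back effect. Both arms are taught from the same guide, so both may improve, and that is the setting in which such a reading fails.

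**Working it through.** **1. The plan's own sample size.** Inputs (Sample size calculation): effect size 0.70, alpha 5%, power 80%. Two-sided testing is assumed because H1 is non-directional. For two independent groups, n = 2 × ((1.960 + 0.842)/0.70)² = 32.04, so 33 per arm (34 by the t-test). The plan states 31. Other readings are further away: 26 one-sided, 19 paired. The stated figure therefore fits a between-arm comparison best, though only approximately. The implied SD is 0.5/0.70 = 0.71 points.

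**2. What each planned test addresses.**

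| Planned test | Compares arms? | Gives a difference at a later visit? |
|---|---|---|
| Homogeneity tests | Yes, for comparability of the groups | No |
| Group main effect | Yes, averaged over three visits | No |
| Group-by-time interaction | Yes, 2-df test | No |
| One-way repeated-measures ANOVA | No | No |
| Paired t-tests with Bonferroni | No | No |

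**3. Dilution of the group main effect.** If teach-back adds nothing at the first meeting and 0.5 points at each later visit, the main effect estimates (0 + 0.5 + 0.5)/3 = 0.33 points, or 0.33/0.71 = 0.47 SD.

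**4. Discordant within-arm results when the arms are identical.** Take n = 40 per arm, the change from visit 1 to visit 3, and alpha 0.05/3 for three pairs of visits. In units of the single-visit SD, the change has SD √(2(1 − ρ)), where ρ is the correlation between visits. Power p in one arm comes from the noncentral t with 39 df. The chance that exactly one arm is significant is 2p(1 − p).

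Example: at ρ = 0.5 and a shared change of 0.4 SD, the SD of change is 1, the noncentrality is 0.4 × √40 = 2.53, the critical value is 2.50 and p = 0.52, so 2 × 0.52 × 0.48 = 0.50.

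| Shared change (SD) | ρ = 0.3 | ρ = 0.5 | ρ = 0.7 |
|---|---|---|---|
| 0.2 | 16% | 21% | 33% |
| 0.3 | 32% | 41% | 50% |
| 0.4 | 47% | 50% | 35% |
| 0.5 | 49% | 38% | 12% |
| 0.6 | 37% | 19% | 2% |

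At ρ = 0.5 the figure is 3%, 6% and 0% for shared changes of 0, 0.7 and 1.0 SD. Half of all discordant results favour teach-back. A direct between-arm test of change stays near 5% in the same setting.

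**5. The same, read only after a significant interaction.** In 20,000 simulated trials per scenario (three visits, linear shared change, equal correlations), the interaction test rejects in about 5%. A significant interaction together with discordant arms occurs in 0–4%. At ρ = 0.5 it is 2.8%, 3.6%, 3.9%, 3.5% and 2.4% for shared changes of 0.2 to 0.6 SD.

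**6. The opposite failure.** With a true between-arm difference of 0.70 SD and both arms rising strongly (1.7 and 1.0 SD), both within-arm tests are significant in more than 99% of simulated trials and so do not show the difference. A direct test of the change between arms detects it with power 0.74, 0.87 and 0.98 at ρ = 0.3, 0.5 and 0.7.

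**7. Whether the missing contrast is feasible.** Adjusted for the first score, SE = √(2(1 − ρ²)/40) = 0.194 SD at ρ = 0.5. The 95% half-width is 0.39 SD, about 0.28 LATCH points (0.23–0.30 points over ρ = 0.7–0.3). With Bonferroni over two visits (97.5% intervals) it is 0.44 SD, about 0.32 points (0.26–0.35). All are below 0.5 points. Even unadjusted, power at 0.70 SD with 40 per arm is 0.87 at alpha 0.05 and 0.80 at alpha 0.025.

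**The case against.** The strongest reply is that H1 is already tested. It says only that teach-back training has an impact, and the interaction term addresses that. If the effect is 0.70 SD at both later visits and nil at the first, the interaction test has power 0.78, 0.91 and 0.99 at correlations of 0.3, 0.5 and 0.7. This stands, and it is why the point is not fatal.

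Next, the within-arm tests mislead only if they are used to compare arms, and no passage says they will be. The phrase about the difference may be loose translation for differences among visits inside each arm. The order of the items also suggests a follow-up to a significant interaction, where the risk is 0–4%, no more than the error rate of the interaction test itself. This stands in part: the document settles neither the reading nor the gate, so the figures in steps 4 and 5 of the working should be read together, and the 50% is a ceiling under assumed inputs. On either reading, though, no between-arm difference is estimated at a later visit.

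Finally, the sample-size sentence speaks of an increase, not explicitly of a difference between arms, and baseline adjustment is only one acceptable way to form the contrast. Both are fair. If the target is a difference in increase, the interaction tests it but still does not give its size with an interval. Unadjusted contrasts would also close the gap, with less precision.

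**Conclusion.** The concern holds and should be fixed. The SAP specifies a follow-up made up entirely of within-arm tests, so the trial can conclude that the arms differ over time but cannot state at which visit or by how much. That conclusion rests on the text alone.

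The main-effect dilution (0.33 instead of 0.5 points) assumes an equal effect at both later visits and none before training. The risk of a false reading is 0–50% if the within-arm tests are read on their own and 0–4% if they are read only after a significant interaction. Both ranges rest on an assumed visit correlation of 0.3–0.7 and an assumed shared change of 0–1.0 SD, neither of which the document gives. As a description of each arm's course, the within-arm tests are acceptable.

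**What to change.** For each scale, replace the stated follow-up with the between-arm mean difference and its confidence interval at day 13–17 and at day 30–42, adjusted for the score taken at the first meeting before training. Apply Bonferroni over the two visits within each scale (alpha 0.025 per test). State whether the intervals are plain 95% or widened to 97.5% to match. Keep the within-arm changes as description, and say that they are not used to infer a difference between arms.

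The cost is a short re-analysis in SPSS of scores already collected, with no new data. Because the Statistical analysis section already reports that the data were found to be normally distributed, the change should be disclosed as a change to the analysis if outcome data have been seen.
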